4.4.2 Immunogenicity

4.4.2.1 Computed Values for Analysis

In order to appropriately manage extreme values ($< \text{LLOQ}$ and $\geq \text{ULOQ}$) for analysis purposes, the following computational rule is applied to the values provided in the clinical database for each BL drawn:

- If a value is $< \text{LLOQ}$, then use the computed value $\text{LLOQ}/2$
- If a value is between $\geq \text{LLOQ}$ and $< \text{ULOQ}$, then use the value

- If a value is \geq ULOQ, then use the computed value ULOQ

4.4.2.2 Seroprotection

Not applicable

4.4.2.3 Fold-rise

The derived endpoint fold-rise is driven by both baseline and post-baseline computed values and is computed as follows. Generally, for extreme values, this algorithm minimizes the numerator and maximizes the denominator.

- If the baseline computed value is $<$ LLOQ and the post-baseline computed value is $<$ LLOQ, then the fold-rise is 1
- If the baseline computed value is \geq LLOQ and the post-baseline computed value is \geq LLOQ, then the fold-rise is post-baseline computed value / baseline computed value
- If the baseline computed value is \geq LLOQ and the post-baseline computed value is $<$ LLOQ, then the fold-rise is (LLOQ/2) / baseline computed value
- If the baseline computed value is $<$ LLOQ and the post-baseline computed value is \geq LLOQ, then the fold-rise is post-baseline computed value /LLOQ

If the computed value is ≥ 4 , then the derived ≥ 4 -fold rises indicator will be "Yes" for that test, otherwise ≥ 4 -fold rises will be "No".

Note: If baseline or post-baseline is missing, then fold-rise is missing.

4.4.2.4 Vaccine Seroresponse

hSBA vaccine seroresponse for serogroups A, C, Y, and W is defined as:

- For a subject with a pre-vaccination titer $<$ 1:8, the post-vaccination titer must be \geq 1:16.
- For a subject with a pre-vaccination titer \geq 1:8, the post-vaccination titer must be at least 4-fold greater than the pre-vaccination titer.

rSBA vaccine seroresponse for serogroups A, C, Y, and W is defined as:

- A post-vaccination titer \geq 1:32 for subjects with pre-vaccination rSBA titer $<$ 1:8.
- A post-vaccination titer \geq 4 times the pre-vaccination titer for subjects with pre-vaccination rSBA titer \geq 1:8

4.4.3 Efficacy

Not applicable

4.4.4 Derived Other Variables

4.4.4.1 Age for Demographics

Age in years: (Date of vaccination - Date of birth +1) / 365.25

4.4.4.2 Subject Duration

The duration of a subject in the study is computed as follows: Maximum (date of last visit, date of term form) – (date of Visit 1) +1.

The duration of a subject in the study including follow-up is computed as follows: Maximum (date of last visit, date of term form, last date of follow-up contact) – (date of Visit 1) +1.

4.4.4.3 Duration of the Study

The duration of the study (until last visit) is computed as follows: Maximum of all subjects (date of last visit, date of termination form) – minimum for all subjects (date of Visit 1) +1.

The duration of the study (including follow-up) is computed as follows: Maximum of all subjects (date of last visit, date of termination form, date of last follow-up contact) – minimum for all subjects (date of Visit 1) +1

4.4.4.4 MAAEs from Visit 1 to Visit 2

MAAEs that occur from Visit 1 to Visit 2 will be recorded as unsolicited AEs on the diary card as part of all unsolicited AEs collected for this post-vaccination period. The unsolicited AEs that have action taken categories 2 (health care provider contact) or 3 (Health care contact + Medication) will be summarized and presented as MAAEs which occurred from Visit 1 to Visit 2.

5 Statistical Methods and Determination of Sample Size

The statistical analyses will be performed under the responsibility of the Sponsor's Biostatistics platform using SAS® Version 9.4 software or later.

The results of the statistical analysis will be available in the final clinical study report (CSR).

For descriptive purposes, the following statistics in Table 5.1 will be presented. The confidence interval (CI) for the single proportion will be calculated using the exact binomial method (Clopper-Pearson method, quoted by Newcombe (7)). For immunogenicity results, assuming that Log₁₀ transformation of the titers / data follows a normal distribution, at first, the mean and the 95% CI will be calculated on Log₁₀ (titers / data) using the usual calculation for normal distribution (using Student's t distribution with n-1 degree of freedom), then antilog transformations will be applied to the results of calculations, in order to provide geometric means (GMs) and their 95% CI.

Table 5.1: Descriptive statistics produced

Baseline characteristics and follow-up description	Categorical data	Number of subjects. Percentage of subjects.
	Continuous data	Mean, standard deviation, quartiles, minimum, and maximum.
Clinical safety results	Categorical data	Solicited: Number and percentage (95% CIs) of subjects. Unsolicited: Number and percentage (95% CIs) of subjects, and number of events.
Immunogenicity results	Categorical data (seroresponse, cutoff)	Number and percentage (95% CIs) of subjects.
	Continuous data (titer / data)	Log ₁₀ : Mean and standard deviation. Anti-Log ₁₀ (work on Log ₁₀ distribution, and anti-Log ₁₀ applied): GM, 95% CI of the GM Graphical representation by Reverse Cumulative Distribution Curve (RCDC).

5.1 Statistical Methods

5.1.1 Hypotheses and Statistical Methods for Primary Objectives

5.1.1.1 Primary Objective 1

5.1.1.1.1 Hypotheses

Equivalence of 3 MenACYW Conjugate Vaccine Lots in Terms of hSBA GMTs

Thirty days after the administration of the MenACYW conjugate vaccine, GMTs of antibodies against meningococcal serogroups A, C, Y, and W in Groups 1, 2, and 3 are equivalent.

Null hypothesis (H₀): $GMT_{(Gi)} / GMT_{(Gj)} \leq 1/2$ or $GMT_{(Gi)} / GMT_{(Gj)} \geq 2$ for any $i \neq j$

Alternative hypothesis (H₁): $1/2 < GMT_{(Gi)} / GMT_{(Gj)} < 2$ for all $i \neq j$

GMT_(Gi) and GMT_(Gj) are the GMTs of antibodies against the meningococcal serogroups A, C, Y, and W for the *i*th and *j*th lots, respectively.

Each of the antigens of A, C, Y, and W serogroups will be tested separately. If the 2-sided 95% confidence interval (CI) of the ratio of the GMTs is $> 1/2$ and < 2 for each pair of lots and each antigen, the non-equivalence assumption will be rejected (i.e. if the equivalence is demonstrated for each pair of lots).

5.1.1.1.2 Statistical Methods

Assuming that Log_{10} transformation of the data follows a normal distribution, the Log_{10} (data) will be used for the statistical analysis, then antilog transformations will be applied to the results of calculations, in order to provide the results in terms of GMTs.

For each of the equivalence hypotheses using the GMT ratios, the statistical methodology will be based on the use of the 2-sided 95% CI of difference in means of post-vaccination Log_{10} transformed titers between pairs of lots with normal approximation. Logarithm transformation of the individual post-vaccination titers will be calculated. Assuming that Log_{10} transformation of the data is normally distributed, the 95% CI for the difference in $\text{Log}_{10}(\text{GMT})$ between pairs of lots will be in the form:

$$\bar{X}_i - \bar{X}_j \pm t(1 - \alpha/2, n_i + n_j - 2) \cdot S \sqrt{1/n_i + 1/n_j}$$

where $\bar{X}_i = \log_{10}(\text{GMT})$ is the mean of $\log_{10}(\text{titer})$ of Group i ,

$S^2 = [(n_i - 1) S_i^2 + (n_j - 1) S_j^2] / (n_i + n_j - 2)$ is the pooled sample variance,

n_i and S_i^2 are the sample size and sample variance of Group i ,

$t(1 - \alpha/2, n_i + n_j - 2)$ is the 100(1- $\alpha/2$) percentile of the t -distribution with degrees of freedom $df = n_i + n_j - 2$.

Equivalence among the three lots will be demonstrated if, for each pair of lots and each antigen, the two-sided 95% CI for the difference in $\log_{10}(\text{GMT})$ lies between $\log_{10}(1/2)$ and $\log_{10}(2)$, or approximately -0.301 and 0.301.

5.1.1.2 Primary Objective 2

5.1.1.2.1 Hypothesis

Non-inferiority of MenACYW Conjugate Vaccine Compared to Menactra[®] in Terms of hSBA Vaccine Seroresponse

Thirty days after the administration of MenACYW conjugate vaccine or Menactra[®], the percentages of subjects who achieve an hSBA vaccine seroresponse (as defined in Section 4.4.2.4) for meningococcal serogroups A, C, Y, and W in Groups 1, 2, and 3 combined are non-inferior to the corresponding percentages in Group 4.

Null hypothesis (H_0): $p_{(G123)} - p_{(G4)} \leq -10\%$

Alternative hypothesis (H_1): $p_{(G123)} - p_{(G4)} > -10\%$

where $p_{(G123)}$ and $p_{(G4)}$ are the percentages of subjects who achieve an hSBA vaccine seroresponse in Groups 1 - 3 pooled and Group 4, respectively.

Each of the serogroups A, C, Y, and W will be tested separately. If the lower limit of the 2-sided 95% CI of the difference between the 2 proportions is $> -10\%$, the inferiority assumption will be

rejected. The overall non-inferiority of this objective will be demonstrated if all 4 individual null hypotheses are rejected.

5.1.1.2.2 Statistical Methods

For the 4 non-inferiority hypotheses using the seroresponse rates, the CI of the difference in proportions will be computed for each of the serogroups A, C, Y, and W using the Wilson Score method without continuity correction (8).

Let $\hat{\theta} = p_{123} - p_4$, then $L = \hat{\theta} - \delta$ and $U = \hat{\theta} + \varepsilon$ are respectively the lower and the upper limits of the CI, where:

$$\delta = Z_{0.025} \sqrt{\left\{ \frac{l_{123}(1-l_{123})}{n_{123}} + \frac{u_4(1-u_4)}{n_4} \right\}}$$

$$\varepsilon = Z_{0.025} \sqrt{\left\{ \frac{l_4(1-l_4)}{n_4} + \frac{u_{123}(1-u_{123})}{n_{123}} \right\}}$$

l_{123} and u_{123} are calculated from the CI of the pooled proportion in Group 1 - 3 given by:

$$\frac{(2n_{123}p_{123} + Z_{0.025}^2 \pm Z_{0.025} \sqrt{(Z_{0.025}^2 + 4n_{123}p_{123}(1-p_{123}))})}{2(n_{123} + Z_{0.025}^2)}$$

l_4 and u_4 are calculated from the CI of the single proportion in Group 4 given by:

$$\frac{(2n_4p_4 + Z_{0.025}^2 \pm Z_{0.025} \sqrt{(Z_{0.025}^2 + 4n_4p_4(1-p_4))})}{2(n_4 + Z_{0.025}^2)}$$

where $Z_{0.025}$ is the upper 97.5th percentile of the standard normal distribution,

$n_{123} = n_1 + n_2 + n_3$ is the total sample size of Groups 1 - 3,

$p_{123} = \frac{\text{total \# of seroresponders in groups 1 - 3}}{n_{123}}$ is the overall seroresponse rate of

Groups 1 - 3.

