
Planned Sample Size:
	
A total of 3300 subjects are planned to be enrolled:
 
 
• Group 1: MenACYW conjugate vaccine (Lot 1): planned = 900 (evaluable = 810) 
 
• Group 1a: 400 subjects 10 to 17 years of age
 
• Group 1b: 500 subjects 18 to 55 years of age
 
 
 
• Group 2: MenACYW conjugate vaccine (Lot 2): planned = 900 (evaluable = 810) 
 
• Group 2a: 400 subjects 10 to 17 years of age
 
• Group 2b: 500 subjects 18 to 55 years of age
 
 
 
• Group 3: MenACYW conjugate vaccine (Lot 3): planned = 900 (evaluable = 810) 
 
• Group 3a: 400 subjects 10 to 17 years of age
 
• Group 3b: 500 subjects 18 to 55 years of age
 
 
 
• Group 4: Menactra®: planned = 600 (evaluable = 540) 
 
• Group 4a: 300 subjects 10 to 17 years of age
 
• Group 4b: 300 subjects 18 to 55 years of age
 
 
 
 
The planned number of subjects is based on a 10% dropout rate allowing around 88% power to reject the primary hypotheses simultaneously assuming the independence between each of the endpoints.

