## 6.5 Randomization and Allocation Procedures

On the day of enrollment, subjects who meet the inclusion/exclusion criteria and sign the ICF (subjects aged 18 to 55 years) or sign the assent form and whose parent / guardian signs the ICF

---

a according to local regulations

(subjects aged 10 to 17 years) will be randomly assigned to Groups 1 through 4 in a 3:3:3:2 ratio, stratified according to age such that Groups 1, 2, and 3 will have approximately 900 subjects (400 subjects 10 to 17 years old and 500 subjects 18 to 55 years old) and Group 4 will have approximately 600 subjects (300 subjects 10 to 17 years old and 300 subjects 18 to 55 years old).

Site staff will connect to the IWRS, enter the identification and security information, and confirm a minimal amount of data in response to IWRS prompts. The IWRS will then provide the group assignment and have the site staff confirm it. The full detailed procedures for group allocation are described in the Operating Guidelines. If the subject is not eligible to participate in the trial, then the information will only be recorded on the subject recruitment log.

Subject numbers that are assigned by the IWRS will consist of an 8-digit string (a 3-digit trial center identifier and a 5-digit subject identifier connected by “-”). For example, Subject 001-00001 is the first subject enrolled in center number 1. Subject numbers should not be reassigned for any reason.

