#### *Non-inferiority of MenACYW Conjugate Vaccine Compared to Menactra® in Terms of hSBA Vaccine Seroreponse*

Thirty days after the administration of MenACYW conjugate vaccine or Menactra®, the percentages of subjects who achieve an hSBA vaccine seroreponsea for meningococcal serogroups A, C, Y, and W in Groups 1, 2, and 3 combined are non-inferior to the corresponding percentages in Group 4.

Null hypothesis ( $H_0$ ):  $p_{(G123)} - p_{(G4)} \leq -10\%$

Alternative hypothesis ( $H_1$ ):  $p_{(G123)} - p_{(G4)} > -10\%$

where  $p_{(G123)}$  and  $p_{(G4)}$  are the percentages of subjects who achieve an hSBA vaccine seroreponse in Groups 1 - 3 pooled and Group 4, respectively. Each of the serogroups A, C, Y, and W will be tested separately. If the lower limit of the 2-sided 95% CI of the difference between the 2 proportions is  $> -10\%$ , the inferiority assumption will be rejected.

For the 4 non-inferiority hypotheses using the seroreponse rates, the CI of the difference in proportions will be computed using the Wilson Score method without continuity correction (35). The overall non-inferiority of this objective will be demonstrated if all 4 individual null hypotheses are rejected.

---

a hSBA vaccine seroreponse for serogroups A, C, Y, and W is defined as:

- For a subject with a pre-vaccination titer  $< 1:8$ , the post-vaccination titer must be  $\geq 1:16$ .
- For a subject with a pre-vaccination titer  $\geq 1:8$ , the post-vaccination titer must be at least 4-fold greater than the pre-vaccination titer.

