5.1.2.1.2 Statistical Methods

For the 4 non-inferiority hypotheses using the seroresponse rates, the CI of the difference in proportions will be computed for each of the serogroups A, C, Y, and W using the Wilson Score method without continuity correction (8). The statistical method as described in Section 5.1.1.2.2 will be used to Groups 1b - 3b pooled and Group 4b.

5.1.2.2 Secondary Objective 2

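### The 3:3:3:2 ratio and the listed age cells disagree within strata; under the cells, the crude Primary Objective 2 difference is shifted whenever adolescents and adults respond differently

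*SAP*

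**What the plan says.** Protocol 6.5 has subjects "randomly assigned to Groups 1 through 4 in a 3:3:3:2 ratio, stratified according to age such that" each lot group has about 900 (400 adolescents and 500 adults), while "Group 4 will have approximately 600 subjects (300 subjects 10 to 17 years old and 300 subjects 18 to 55 years old". The same cells appear in the Protocol Synopsis, Protocol 5.1.1 and SAP 3.1, each time beside the 3:3:3:2 ratio. On how allocation was carried out, Protocol 6.5 says only: "The full detailed procedures for group allocation are described in the Operating Guidelines".

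For Primary Objective 2, SAP 5.1.1.2.2 says "the CI of the difference in proportions will be computed for each of the serogroups A, C, Y, and W using the Wilson Score" method. It defines the MenACYW rate as all seroresponders in Groups 1 to 3 divided by their total sample size, and takes the Newcombe/Wilson limits from that single proportion and the one for Group 4. Protocol 12.1.1.2 agrees: "the CI of the difference in proportions will be computed using the Wilson Score method without continuity correction". Neither has an age stratum or weight. The margin is -10%, and all serogroups count: "The overall non-inferiority of this objective will be demonstrated if all 4 individual null hypotheses are rejected" (SAP 5.1.1.2.1).

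Age enters only in Secondary Objectives 1 and 2, which repeat the test within each age group (for adults, SAP 5.1.2.1.2: "The statistical method as described in Section 5.1.1.2.2 will be used to Groups 1b - 3b pooled and Group 4b"), and in the descriptive age-group output of SAP 5.1.4. No age-stratified version of the pooled comparison is planned.

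**The concern.** There are two linked problems. First, a ratio described as stratified by age should hold in each stratum, and the listed cells do not follow it. A reader cannot tell from the documents which version the allocation system used.

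Second, if the cells were used, the probability of receiving Menactra differs between adolescents and adults. Age is then associated with treatment by design, and randomization does not balance it across the pooled arms. A crude difference mixes the vaccine effect with the difference in age mix. A larger sample does not shrink this.

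Primary Objective 2 is confirmatory. Its estimate could move toward or away from the margin for a reason unrelated to the vaccine, so either the false-positive rate or the power would differ from what the 95% interval implies.

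**Working it through.** **1. The plan's own totals.** 3300 x 3/11 = 900 and 3300 x 2/11 = 600. With 10% dropout, 900 x 0.9 = 810 and 600 x 0.9 = 540, which agrees with the Synopsis entry for Menactra, "planned = 600 (evaluable = 540". The totals reproduce exactly. The joint power of about 88% cannot be reproduced because its inputs are blacked out.

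**2. Cells against ratio.**

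| Stratum | Total | Listed, per lot / Menactra | 3:3:3:2 would give | Lot-to-Menactra ratio as listed |
|---|---|---|---|---|
| 10 to 17 years | 1500 | 400 / 300 | 409 / 273 | 1.33 |
| 18 to 55 years | 1800 | 500 / 300 | 491 / 327 | 1.67 |
| All | 3300 | 900 / 600 | 900 / 600 | 1.50 |

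The word approximately in Protocol 6.5 does not cover 300 against 273 or 300 against 327.

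**3. Age mix under the cells.** The adolescent share is 1200/2700 = 44.4% in pooled MenACYW and 300/600 = 50.0% in Menactra, a difference of -0.0556. With 3:3:3:2 in each stratum both arms would be 1500/3300 = 45.5% adolescent.

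**4. Shift.** Let the true vaccine difference be d in both age groups, with Menactra rates a (adolescents) and b (adults). Then

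crude difference = [0.444(a + d) + 0.556(b + d)] - [0.5a + 0.5b] = d - 0.0556 x (a - b).

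Age gaps of 5, 10 and 20 points shift the estimate by 0.28, 0.56 and 1.11 points. The shift is downward (conservative) if adolescents respond better and upward (anti-conservative) if adults do.

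**5. Error rate for one serogroup.** I simulated 400,000 trials per scenario at 90% evaluable. The listed cells become 1080/1350 (MenACYW adolescents/adults) against 270/270 (Menactra); 3:3:3:2 cells become 1105/1325 against 245/295. Assumptions: a Menactra mean over the two strata of 75%, stratum rates of 75% plus or minus half the gap, and a true difference of -10 points in both strata. A pass is a lower limit above -10%.

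| Age gap | Crude SAP interval, listed cells |
|---|---|
| none | 2.6% |
| adults 5 points better | 3.5% |
| adults 10 better | 4.6% |
| adults 20 better | 7.5% |
| adolescents 10 better | 1.3% |
| adolescents 20 better | 0.6% |

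For comparison:
- A Newcombe interval stratified with Mantel-Haenszel weights stays at 2.3 to 2.6% over these gaps, and a Mantel-Haenszel-weighted Wald interval at 2.2 to 2.4%.
- With 3:3:3:2 within strata, the crude interval stays at 1.9 to 2.6% for gaps of up to 30 points either way.
- With a Menactra mean of 65% instead, the crude figures for adults 10 and 20 points better are 4.4% and 6.8%.

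**6. Error for the whole objective.** One serogroup is at the margin, the other three are at a common true difference, serogroups are independent, and the age gap is the same in all four. Error = (error at the margin) x (power of another serogroup) cubed.

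| Other three at | Adults 10 better | Adults 20 better |
|---|---|---|
| 0 | 0.0458 x 0.9997^3 = 4.6% | 0.0751 x 0.9999^3 = 7.5% |
| -2.5 | 0.0458 x 0.9831^3 = 4.4% | 0.0751 x 0.9935^3 = 7.4% |
| -5 | 0.0458 x 0.7931^3 = 2.3% | 0.0751 x 0.8708^3 = 5.0% |

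**7. Power for one serogroup.** With adolescents 20 points better, power at a true -5 is 49% crude against 70% stratified; at a true 0 it is 99.6% against 99.9%. With no gap, stratifying costs nothing: 70.2% and 70.3% at a true -5.

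**The case against.** **The ratio may be meant for the arm totals only**, with the cells setting the strata. The text allows this. But the arms then differ in age mix by design, so that reading settles the wording problem only by making the shift real whenever the age groups differ.

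**The null as written concerns the pooled percentages.** Against a true pooled difference of exactly -10%, the crude interval is calibrated, passing 2.3 to 2.6% of the time for gaps up to 20 points either way. This is correct: the inflated figures above refer to a different null, a deficit of 10 points within each age group. But a pooled difference between arms with different age mixes is not a vaccine effect, and the objective is about the vaccine.

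**The effect is small, conditional and of unknown sign.** This stands as a limit on weight. Inflation needs adults to respond better and a serogroup at the margin. When the other serogroups are also weak, the objective-level error can fall below 2.5%. The power loss matters only when the true difference is well below zero.

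**The age-specific tests protect against a false conclusion.** At a true -10 in both strata with adults 10 to 20 points better, the crude test and both age-specific tests all pass for a given serogroup only about 0.07% of the time. That is a real safeguard for interpretation. However, those are secondary tests, and the primary conclusion does not depend on them.

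**Conclusion.** The concern holds and should be fixed. The mismatch between ratio and cells is plain arithmetic. The shift in the primary estimate is conditional: it needs the listed cells to have been used and seroresponse to differ by age. Its size is 0.0556 times the age gap, so about half a point per 10 points of gap.

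Under the stated assumptions, the per-serogroup error is 4.6% or 7.5% if adults respond 10 or 20 points better, and 1.3% or 0.6% if adolescents do, against 2.6% with no gap. The gaps and the Menactra mean are assumptions, because no visible passage gives rates by age. If 3:3:3:2 was applied within strata there is no shift, and only the text of Protocol 6.5 needs correcting.

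Lot consistency is unaffected, since every lot has the same 400/500 mix, and so are Secondary Objectives 1 and 2. The pooled GMT ratio of Secondary Objective 4 has the same imbalance: an age gap of 0.3 on the log10 scale would multiply it by 10^(-0.0556 x 0.3) = 0.96.

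**What to change.** - In Protocol 6.5, state the allocation ratio actually used in each age stratum, so that it agrees with the cell sizes.
- In SAP 5.1.1.2.2 and Protocol 12.1.1.2, make the primary difference and interval stratified by the two randomization age strata, for example Newcombe/Wilson with Mantel-Haenszel weights or stratified Miettinen-Nurminen. Write out the formula, and keep the crude Wilson interval as a sensitivity analysis.
- Apply the same adjustment to the GMT ratio in SAP 5.1.2.4.2.
- Make the change before database lock and unblinding, and record it in SAP 5.7, which now reads as not applicable.

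The cost is wording and a few lines of code, with no new data or subjects. The Protocol edits need an amendment, and Protocol 5.4 requires IEC/IRB approval and submission to regulators if it is substantial. SAP 5.2 shows that the plan was still being revised before lock, although those additions were analysis sets rather than a new primary estimator. If the primary method cannot be changed, a prespecified age-stratified sensitivity analysis is the minimum.
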